8.10 Replacement/Addition of Subjects

Should there be, during the DLT evaluation period in the phase I part of the study, a major deviation from the protocol affecting the DLT evaluation for a reason other than an adverse event classified as a DLT or if DLT cannot be evaluated appropriately, that subject can be excluded from the DLT evaluation and a new subject can be enrolled and added to that cohort.

8.11 Contraindicated drugs/therapies

The drugs and therapies shown below are contraindicated from informed consent until discontinuation of protocol treatment. The investigator or the subinvestigator should instruct the subjects not to use any drugs including over-the counter drugs other than the prescribed drugs without prior consultation.

- Chemotherapy for primary disease other than protocol treatment
- Hormone therapy for primary disease
- Immunotherapy for primary disease
 - Cellular immunotherapy
 - Vaccine therapy
 - Cytokine therapy
 - Except for G-CSF
 - Biological Response Modifiers (BRM) therapy
 - Antibody therapy
 - Gene therapy
- Other antibody therapy (except for denosumab)
- Flucytosine (antifungal)

CONFIDENTIAL

- Radiotherapy for primary disease
Except for treatment for pain relief of bone metastasis site is allowed.
- Hyperthermia therapy for primary disease
- Study drug and unapproved drug

8.12 Recommended supportive care and combination medications

The supportive care and concomitant medications shown below are recommended during the study period (from obtaining consent until discontinuation of protocol treatment). The absence of supportive care or concomitant medications does not constitute a protocol deviation.

- Neutropenia
Granulocyte colony stimulating factor (hereinafter referred to as G-CSF) should be administered. The type of G-CSF products administered should depend on the insurance coverage.
- Nausea/vomiting
Premedication including prophylactic administration of antiemetics is allowed. Premedication with 5-HT3 (serotonin) receptor antagonists, NK1 (neurokinin 1) receptor antagonists, steroids, and antihistamines may be carried out using the method employed at each study site.
- Diarrhoea
Fluids and electrolyte balance will be followed adequately, and suitably supplemented, as necessary. If careful observation suggests that it is necessary, administration of an antidiarrheal such as loperamide hydrochloride may be considered.
- Allergic reaction
Treatment with adrenal corticosteroids, antihistamines, etc. may be considered at the time of onset or for premedication at the start of the subsequent course. Careful administration of panitumumab by slowing the infusion speed may be considered.
- Pulmonary fibrosis (interstitial pneumonia)
If it occurs, it should be treated according to the severity (e.g., steroid pulse therapy).
- Hepatitis B
Refer to JSH Guidelines for the Management of Hepatitis B virus infection (http://www.jsh.or.jp/doc/guidelines/HBV_GL_ver2.201406.pdf) and take appropriate action and monitoring.
- Others
Drugs for treatment of adverse events may be coadministered at the discretion of the investigator or the subinvestigator. Symptomatic therapies which have been continued from before the start of this study are allowed.

In addition, it is recommended that the supportive care shown below be performed at the discretion of the investigator or the subinvestigator when any of panitumumab-related adverse events listed below is observed. The absence of supportive care does not constitute a protocol deviation.

- Skin disorder
 - Tetracycline antibiotic (e.g. oral minocycline)

CONFIDENTIAL

- External salicylic acid petrolatum (10%)
- External steroid therapy (example)
 - Face: hydrocortisone butyrate (0.1%)
 - Trunk: difluprednate (0.05%)
- Moisturizer (example): heparin analog lotion
- Sunscreen (example): not containing 4-aminobenzoic acid, SPF (Sun Protection Factor) 30, PA (Protection grade of UVA)++. Apply before going out to block ultraviolet rays (UVA and UVB).

Dermatopathy prevention with humectants, suntan lotion, antibiotic or external steroids may be carried out using the method employed at each study site, based on non-Japanese²⁹⁾ and Japanese reports³⁰⁾, etc.

- Electrolyte abnormality (e.g., hypomagnesaemia, hypocalcaemia)
 - ECG: ECG may be performed to determine whether there are abnormal ECG findings requiring treatment such as significant QTc prolongation. When any abnormal ECG findings requiring treatment are observed, suspension of panitumumab should be considered irrespective of the serum magnesium concentration.
 - Magnesium supplementation (example): intravenous infusion of magnesium sulfate (10 mmol) over 60 min

8.13 Recommended follow-up therapy

Approved drugs (e.g., regorafenib) should be used as appropriately as possible.

9.0 PROTOCOL, EVALUATION ITEMS AND PROCEDURES FOR OBSERVATIONS

9.1 Study calendar

The investigator or the subinvestigator should collect data according to “Table 9.a Study calendar (phase I part of the study)” in the phase I part of the study and “Table 9.b Study calendar (phase II part of the study)” in the phase II part of the study. The same investigator or the subinvestigator should perform tests/observations/evaluation of subjects in principle. For the allowance range of protocol treatment and various laboratory tests, see “Table 9.c Allowance range for protocol treatment and laboratory tests”

Table 9.a Study calendar (phase I part of the study)

Item	At enrollment	Protocol treatment period						Follow-up period [#]
		Course 1			Second and later courses		Discontinuation of protocol treatment †	
Reference day: Number of days counted from the first day of each course	-14, -1	1	8	15	22	1	15	
Informed consent obtained* ¹	●							
Patient Background	●							
RAS status* ²	●							
Clinical findings* ³	●	●	●	●	●	●	●	
Height* ²	●							
Body weight* ⁴	●* ⁷	○	○	○	○	○	○	
ECOG P.S. * ³	●* ⁷	●	○	○	○	●	○	●
Compliance* ³		●	○	○		●	○	
Hematology* ⁵	●* ⁷	●	●	●	●	●	●	
Serum chemistry* ⁵	●* ⁷	●	●	●	●	●	●	
Immunology (HBs antigen)* ⁶	●							
Tumor marker		●* ⁸			<- ●* ⁹ ->		●	
Imaging tests (thoracoabdominal-pelvic CT/MRI)	●* ¹⁰				<- ●* ⁹ ->		○* ¹¹	○
Follow-up treatment								●
Survival survey								●
Adverse events	-	<- ● ->						○

●: Mandatory, ○: Perform as necessary

†: Perform within 28 days of discontinuation or earlier date than start of follow-up treatment, as well as possible.

#: Perform every 6 months as a guide with protocol discontinuation date as starting point.

*1: Consent must be obtained before enrollment. Further, consent should be obtained after RAS status has been identified.

*2: Values obtained after the diagnosis of colorectal cancer may be used.

*3: When the visit day is the treatment day, this will be done before administration.

*4: Measurement is not mandatory during protocol treatment period. Even if measured, it is unnecessary to record in the CRF.

*5: Testing will be performed from 2 days before to the day of the visit during each course.

*6: Test results from up to one year before obtaining consent may be used. It is unnecessary to record this in the CRF. However, follow JSH Guidelines for the Management of Hepatitis B virus infection for the measurement of HBs antibody, HBc antibody and HBV-DNA.

*7: If done within 14 days before enrollment, results from before obtaining informed consent may be used.

CONFIDENTIAL

- *8: If it has been performed within 28days before treatment day, the test for Course 1 may be omitted.
- *9: Measure once every 8 weeks (56 days) with Day 1 of Course 1 as starting point. However, reduce the frequency to once every 12 weeks (84 days) when one year has passed since initiation of protocol treatment.
- *10: Imaging test will be performed within 4 weeks (28 days) prior to enrollment (including the same day of week as the day of enrollment). The results of imaging diagnosis/test performed before obtaining consent may be used if it is performed within 4 weeks (28 days) prior to enrollment.
- *11: This is only done when the subject is discontinued for a reason other than imaging results (PD).

Table 9.b Study calendar (phase II part of the study)

Item	At enrollment	Protocol treatment period						Follow-up period [#]
		Course 1		Second and later courses		Discontinuation of protocol treatment [†]		
Number of days counted from the first day of each course	-14, -1	1	15	22	1	15		
Informed consent obtained* ¹	●							
Patient Background	●							
RAS status* ²	●							
Clinical findings* ³	●	●	●	●	●	●	●	
Height* ²	●							
Body weight* ⁴	● ^{*7}	○	○	○	○	○		
ECOG P.S. * ³	● ^{*7}	●	○	○	●	○	●	
Compliance* ³		●	○		●	○		
Hematology* ⁵	● ^{*7}	●	●	●	●	●	●	
Serum chemistry* ⁵	● ^{*7}	●	●	●	●	●	●	
Immunology (HBs antigen)* ⁶	●							
Tumor marker		● ^{*8}			<-●* ⁹ ->		●	
Imaging tests (thoracoabdominal-pelvic CT/MRI)	● ^{*10}				<-●* ⁹ ->	○ ^{*11}	○	
Follow-up treatment								●
Survival survey								●
Adverse events	-			<-●->				○

●: Mandatory, ○: Perform as necessary

†: Perform within 28days of discontinuation or earlier date than start of follow-up treatment, as well as possible.

#: Perform every 6 months as a guide with protocol discontinuation date as starting point.

*1: Consent must be obtained before enrollment. Further, consent should be obtained after RAS status has been identified.

*2: Values obtained after the diagnosis of colorectal cancer may be used.

*3: When the visit day is the treatment day, this will be done before administration.

- *4: Measurement is not mandatory during protocol treatment period. Even if measured, it is unnecessary to record in the CRF.
- *5: Testing will be performed from 2 days before to the day of the visit during each course.
- *6: Test results from up to one year before obtaining consent may be used. It is unnecessary to record this in the CRF. However, follow JSH Guidelines for the Management of Hepatitis B virus infection for the measurement of HBs antibody, HBc antibody and HBV-DNA.
- *7: If done within 14 days before enrollment, results from before obtaining informed consent may be used.
- *8: If it has been performed within 28 days before treatment day, the test for Course 1 may be omitted.
- *9: Measure once every 8 weeks (56 days) with Day 1 of Course 1 as starting point. However, reduce the frequency to once every 12 weeks (84 days) when one year has passed since initiation of protocol treatment.
- *10: Imaging test will be performed within 4 weeks (28 days) prior to enrollment (including the same day of week as the day of enrollment). The results of imaging diagnosis/test performed before obtaining consent may be used if it is performed within 4 weeks (28 days) prior to enrollment.
- *11: This is only done when discontinuation is for a reason other than imaging results (PD).

Table 9.c Allowance range for protocol treatment and laboratory tests

Performed items	Protocol specification	Allowance range
Clinical Laboratory test values (During protocol treatment)	Course 1: Day 1, 8, 15, 22 (phase I part of the study) or Day 1, 15, 22 (phase II part of the study) Course 2: Day 1, 15	From Day -2 before scheduled day (However, Mg is tested once per course.)
Protocol treatment	Day 1, 15, 29 (Day 29 is equal to Day 1 of next course)	Scheduled day \pm 3 days
Tumor markers and imaging tests (during protocol treatment)	Protocol treatment \leq 1 year: 8 weeks (56 days)	Scheduled day \pm 1 week (7 days)
	Protocol treatment > 1 year: 12 weeks (84 days)	Scheduled day \pm 2 week (14 days)

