8.4 Criteria for administration

In principle, the day (Day 29) that is 4 weeks after the starting day of treatment (Day 1) in the previous course will be Day 1 of the subsequent course (however, if the actual starting day is the next morning, the day before the starting day will be Day 1). Postponement or acceleration due to

holidays is allowed. See "Table 9.c Allowance range for protocol treatment and laboratory tests".

It should be confirmed that all of the criteria for initiation of protocol treatment (Table 8.d, Table 8.e) are satisfied on the starting day of treatment of each course. However, the latest data obtained from 2 days before treatment to the starting day of treatment may be used as test value.

Treatment will be postponed when any of the criteria for each drug is not met, and will be started after confirming that the symptom and laboratory data satisfy all of the criteria, and if only one drug satisfies the criteria for start of treatment then monotherapy with that drug may be allowed. However, at the starting point of the second course of the phase I part, both drugs are required to meet the treatment initiation criteria. If start of treatment with TAS-102 is postponed, the starting day thereafter (if the actual starting day is next morning, the day before) will be Day 1 of the course and that will be the schedule starting point, and if treatment with TAS-102 is determined to be discontinued and monotherapy with panitumumab is to be continued, the starting day of monotherapy with panitumumab will be defined as the start of course (Day 1), and the course will be defined as to give panitumumab on Day 1 and Day 15 between Day 1 and Day 28. However, while monotherapy with panitumumab is ongoing and treatment does not start beyond 42 days from scheduled start of treatment (starting day of treatment of previous course as Day 1, if treatment does not start by Day 57), protocol treatment will be discontinued. Postponement of start of treatment due to holidays is allowed.

Also, if start of treatment with panitumumab is postponed or discontinued, the starting day of treatment with TAS-102 (if the actual starting day is next morning, the day before) will be Day 1 of the course and that will be starting point for the schedule thereafter. However, while monotherapy with TAS-102 is ongoing and treatment does not start beyond 28 days from scheduled start of

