treatment (starting day of treatment of previous course as Day 1, if treatment does not start by Day 57), protocol treatment will be discontinued. Postponement of start of treatment due to holidays is allowed.

[figure not shown]

Table 8.d. Criteria for initiation of treatment with panitumumab

Item	Criteria for initiation
Skin symptom (e.g., rash acneiform, dry skin, paronychia)	\leq Grade 2
Hypomagnesaemia *	\leq Grade 2
Treatment may be postponed when suspension is needed at the discretion of the investigator or the subinvestigator due to adverse events not listed above.	

*: When accompanied by abnormal ECG findings requiring treatment such as significant QTc prolongation, discontinuation or suspension of panitumumab should be considered irrespective of the severity of hypomagnesaemia.

Table 8.e Criteria for initiation of treatment with TAS-102

Item	Criteria for initiation
Hemoglobin concentration	\geq 8.0 g/dL
Neutrophil count	$\geq 1.5 \times 10^3 \mu\text{L}$
Platelet count	$\geq 7.5 \times 10^4/\mu\text{L}$
Total bilirubin	$\leq 1.5 \text{ mg/dL}$
AST	$\leq 100 \text{ IU/L}$
ALT	($\leq 200 \text{ IU/L}$ with liver metastasis)
Serum creatinine	$\leq 1.5 \text{ mg/dL}$
Peripherial sensory neuropathy	\leq Grade 2
Other non-hematological toxicity	(excluding alopecia, dygeusia, pigmentation, underlying disease related symptoms) \leq Grade 1

Treatment may be postponed when suspension is needed at the discretion of the investigator or the subinvestigator due to adverse events not listed above.

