Note 10) Subjects should be followed vigilantly, including HBV DNA monitoring, for at least 12 months after terminating nucleotide analogue treatment. The follow-up should be based on the Precautions for Use in the package insert of the nucleotide analogue used. Nucleotide analogue treatment should be resumed immediately when HBV DNA reaches 2.1 log copies/mL or higher in subjects being followed.

Table 9.f Clinical laboratory tests performed during the protocol treatment period

Hematology	Serum chemistry	Tumor markers
Neutrophil count *	Total bilirubin *	CEA**, †
Platelet count *	ALT*	
Hemoglobin content *	AST*	
	Creatinine *	
	Mg ***	
	Albumin *	
	Na*	
	K*	
	Ca*	

*: The test in Course 1 may be omitted when the pre-entry test had been performed within 2 days before treatment in Course 1. The test in Course 1 will be performed before administration in Course 1 when the pre-entry test had been performed more than 2 days before treatment in Course 1.

**: If it had been conducted within 28 days before treatment day, it may be omitted.

***: May be measured once during each course.

†: Measure every 8 weeks (56 days) with Day 1 of Course 1 as starting point. However, when 1 year has passed since initiation of protocol treatment, once every 12 weeks (84 days).

Table 9.g Laboratory tests performed at the time of discontinuation

Hematology	Serum chemistry	Tumor markers
Neutrophil count	Total bilirubin	CEA*
Platelet count	ALT	
Hemoglobin content	AST	
	Creatinine	
	Mg	
	Albumin	
	Na	
	K	
	Ca	

*: If ≥ 28 days has not passed since the last measurement, the test can be omitted.

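### No fresh serum magnesium is required before the Day 15 panitumumab infusion, although Table 8.f holds the next dose for Grade 3 or higher hypomagnesaemia

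*Protocol*

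**What the plan says.** - **Dosing.** Section 2.0 and Table 8a schedule panitumumab on Day 1 and Day 15 of a 28-day course. Table 9.c allows 3 days either side of the treatment days, listed as "Day 1, 15, 29 (Day 29 is equal to Day 1 of next course").
- **Chemistry.** Tables 9.a and 9.b make serum chemistry mandatory on Day 1 and Day 15 of every course, and Table 9.f lists Mg under serum chemistry. Mg is then taken out of that schedule twice: Table 9.c says "However, Mg is tested once per course", and Table 9.f footnote *** says "May be measured once during each course".
- **Starting a course.** Table 8.d ("Criteria for initiation of treatment with panitumumab") requires hypomagnesaemia of Grade 2 or lower. Section 8.4 asks for confirmation that the criteria "are satisfied on the starting day of treatment of each course", and adds that "the latest data obtained from 2 days before treatment to the starting day of treatment may be used as test value".
- **Holding a dose.** Table 8.f governs the next panitumumab dose, not the next course. For skin disorder of Grade 3 or higher it calls for suspension and then a one-level reduction, with 6 mg/kg still allowed after recovery to Grade 2 or less within 42 days. Hypomagnesaemia of Grade 3 or higher is the next row. Its action cell is blank in the text available and is read here as merged with the skin-disorder cell, which fits the table's title and Table 8.d.

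**The concern.** The hold rule works per infusion, while the required test works per course. With two infusions and one required magnesium value, the rule has no current laboratory input at one infusion in each course. Table 8.f sets no limit on the age of the value relied upon.

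The stake is patient safety at a single dose. A subject who moves to Grade 3 or higher between Day 1 and Day 15 could receive the Day 15 infusion because nobody was required to look. The sponsor itself treats this toxicity as dose-relevant: it is one of the two named criteria for starting panitumumab, and footnotes to Tables 8.d and 8.f link it to QTc prolongation.

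**Working it through.** The plan gives no figure to reproduce. The check is a count and an interval calculation.

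**1. Tests against infusions.** Infusions per course = 2 (Days 1 and 15). Required Mg tests per course = 1 (Tables 9.c and 9.f). Infusions with no required Mg value of their own = 2 − 1 = 1 per course.

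**2. Which infusion lacks the value.** Table 9.f names no day. Section 8.4 needs a value no more than 2 days old at course start, so a site doing only the minimum must spend its one test there. Day 15 is left without one. This step is an inference from 8.4.

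**3. Age of the value at Day 15.**
- Nominal: 15 − 1 = 14 days, plus 0 to 2 days for the sampling window, gives 14 to 16 days.
- With the 3-day allowance: shortest 14 − 3 + 0 = 11 days; longest 14 + 3 + 2 = 19 days.

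Only one allowance is applied, because Day 15 is taken from the actual Day 1. The study calendar's reference day is "Number of days counted from the first day of each course". Section 8.4 says of a postponed TAS-102 start that the actual starting day "will be Day 1 of the course and that will be the schedule starting point"; that sentence covers the postponed case only, so it supports the reading without settling it.

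**4. Does other text close the gap?**

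| Text | What it provides | Serum Mg required before a routine Day 15 dose? |
|---|---|---|
| Tables 9.a and 9.b, serum chemistry | Mandatory on Day 15 | No; Mg is expressly exempted |
| 9.2.5 Clinical findings | Examination before treatment; list includes hypomagnesaemia | No laboratory value is specified |
| 8.5.1 | Confirmation before resuming | No; applies after a hold or skipped dose |
| 8.12 | ECG as an option | No |
| Tables 8.d and 8.f | Investigator may postpone or suspend at discretion | No |
| 8.0 | Refers to the package insert | Not in the documents; cannot be checked |

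**5. Context rates.** Whole-treatment hypomagnesaemia of Grade 3 or higher:
- Table 4.b, Japanese monotherapy study: 0/52.
- Table 4.c, surveillance: 61/1,254 = 4.9% with monotherapy; 62/1,831 = 3.4% with chemotherapy.

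None of these describes new onset between Day 1 and Day 15, so they cannot be turned into a number of missed holds.

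**6. Extra assays under the fix.** 168 / 28 = 6 courses. 6 × 1 × 52 = 312; for the maximum of 58 subjects, 6 × 1 × 58 = 348. Both assume that every subject completes six courses with a Day 15 infusion, so they are ceilings for that period.

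**The case against.** The strongest reply is that the exemption is deliberate and is only a minimum. It appears in two tables, sites may test more often, and Day 15 is not unguarded. Clinical findings are mandatory that day before dosing. The investigator can suspend, an ECG is available, and the next course start brings a required check. Section 8.0 also points to the package insert, which may carry its own monitoring advice. The list in 9.2.5 includes laboratory-defined items such as reduced neutrophil and platelet counts, so its call to confirm hypomagnesaemia need not mean a bedside impression only. Finally, the Japanese monotherapy study recorded no Grade 3 or higher case in 52 patients, and nothing in the documents shows that the chosen interval has caused harm.

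Much of this stands, and it limits the weight of the point. A reader might infer that Day 15 dosing is unmonitored, or that the 3.4% to 4.9% rates measure the holds that would be missed. The documents support neither: the safeguards are real, and the rates cover whole treatment. What does not stand is the suggestion that the safeguards already supply the value. None of the text available requires a serum Mg result before an ordinary Day 15 infusion, and the list in 9.2.5 does not override an exemption stated twice. The insert cannot be assessed from the documents.

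**Conclusion.** The gap is real but modest. A compliant site may give the Day 15 dose on a magnesium value about 14 to 16 days old (11 to 19 at the limits of the allowance), although the Table 8.f hold applies to that dose. At most one infusion per course is exposed before the next course-start check, which should find an abnormality that persists.

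The conclusion rests on three readings: the single test falls at course start, the hypomagnesaemia row of Table 8.f shares the skin-disorder action, and Day 15 is counted from the actual Day 1. The first two support the gap itself; the third affects only the 11-to-19-day range.

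A reader might also infer damage to the trial's results. The documents do not support that. The primary endpoint is unaffected. The two descriptive outputs touched, the laboratory shift table (SAP 7.2.6.2) and the days to onset of Grade 3 or higher hypomagnesaemia (SAP 7.2.6.3), remain computable.

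**What to change.** Keep the existing minimum and add Day 15. In Table 9.c and in Table 9.f footnote ***, write: *Mg is tested at least once per course, at Day 1 (sample taken that day or in the preceding 2 days), also in courses in which panitumumab is withheld; and, in addition, before the Day 15 panitumumab infusion, with the same 2-day window. Not required on Day 8 or Day 22.* The hold thresholds stay as they are.

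The minimum should not be replaced by a rule tied only to infusions. Sections 8.4 and 8.5.1 allow courses of TAS-102 alone, and such a rule would drop the test in those courses, including for subjects held because of hypomagnesaemia.

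The cost is at most one extra Mg assay per course on the existing Day 15 draw, with no new visit. The ceiling over 168 days is 312 assays for 52 subjects or 348 for 58. Discontinuations will lower this; treatment beyond 168 days would add to it, since section 8.7 sets no limit on the number of doses. A protocol amendment under section 6.4 is also needed, with notice to sites, investigator agreement, and ethics re-review where necessary. Some Day 15 doses may be held as a result, as Table 8.f intends.

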8.5 Criteria for protocol treatment change

8.5.1 Criteria for suspension/dose reduction of panitumumab

The criteria for suspension/dose reduction and doses of panitumumab are shown in Table 8.f and Table 8.g, respectively.

Table 8.f Criteria for suspension/dose reduction of panitumumab

Item	Grade	Dose adjustment for the next dose of panitumumab
Skin disorder	≥ 3	Dose reduction by 1 level after suspension However, treatment at a dose of 6 mg/kg is allowed without dose reduction when it recovers to Grade 2 or less within 6 weeks (42 days) .
Hypomagnesaemia *	≥ 3	
Pulmonary fibrosis (interstitial pneumonia)	≥ 2	Discontinue protocol treatment
Infusion reaction (reaction from injection) **, ***	≥ 3	Discontinuation (no resumption)

Dose reduction/suspension is allowed as necessary at the discretion of the investigator or the subinvestigator due to adverse events not listed above.

*: When accompanied by abnormal ECG findings requiring treatment such as significant QTc prolongation, discontinuation or suspension of panitumumab should be considered irrespective of the severity of hypomagnesaemia.

**: Allergic reaction, anaphylactoid reaction, and chills, fever, and dyspnea occurring within 24 hours after the initial dose

***: If infusion reaction is observed, immediately discontinue administration. The course may be resumed at the discretion of the study site. In the event that Grade 1 or 2 infusion reaction occurs during infusion, careful administration will be allowed after appropriate supportive therapy has been given or infusion speed has been decreased by 50%, etc., upon administration of subsequent course.

Table 8.g Doses of panitumumab

Dose reduction level	Panitumumab
Initial dose	6 mg/kg
-1	4.8 mg/kg
-2	3.6 mg/kg
-3	Discontinuation (no resumption)

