The administration of panitumumab may be postponed (skipped) and only TAS-102 therapy performed when the subject meets the panitumumab suspension criteria (in this case, the day of starting the next course (Day 1) will be the day of starting TAS-102 therapy). When the actual day of initiating administration starts on the morning of the next day, the day before starting administration will be Day 1. For the next dose of panitumumab, treatment will be resumed after it is confirmed that the subject does not meet the criteria for suspension of panitumumab, but if panitumumab cannot be administered for more than 28 days after the scheduled day of treatment initiation, panitumumab treatment will be discontinued.

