TAS-102 treatment will be resumed after it is confirmed that the subject meets the criteria for initiation of TAS-102 treatment (however, when the subject satisfies the criteria for initiation of treatment from Day 13 to Day 28 of the suspension period, treatment will be resumed on Day 29). However, if TAS-102 cannot be administered for more than 28 days from the scheduled day of initiation of treatment, treatment with TAS-102 will be discontinued. (At this time, the day of initiating panitumumab monotherapy after it is determined that treatment with TAS-102 will be discontinued will be defined as the day for starting the course (Day 1), and the course will be defined as the administration of panitumumab between Day 1 and Day 28 on Days 1 and 15.)

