When a subject has an existing symptom that is transient (e.g., asthma, epilepsy) and incidence of the symptom is increased, or the symptom becomes serious or severe, it should be recorded as an adverse event. When a subject has a chronic disease (e.g., cataract, rheumatoid arthritis) and the symptom is aggravated more than anticipated, it should be recorded as an adverse event. The investigator or the subinvestigator should record in a way that will make the reported adverse event name be recognized as a change from baseline (e.g., aggravation of XX).

Change of severity of adverse events:

When the severity of an adverse event has changed, the event should be recorded once at the highest degree of severity (grade based on the CTCAE [Japanese edition JCOG version 4.03]), and should be recorded in each protocol treatment course.

Previously planned surgery or treatment:

Surgery or treatment planned before initiation of protocol treatment is not considered an adverse event. However, when the existing symptom is aggravated to require emergency surgery or treatment, the condition or the event is considered an adverse event. A complication which resulted from previously planned surgery is reported as an adverse event.

Non-urgent surgery or treatment:

Non-urgent surgery or treatment that does not induce a change in the condition of a subject (cosmetic surgery, etc.) is not considered an adverse event. However it should be recorded in the source documents. Complications due to a non-urgent surgery should be reported as an adverse event.

Progressive Disease (PD):

PD should be considered lack of efficacy, not an adverse event. In addition, the single fact of PD does not necessarily constitute a serious adverse event. However, if a clinical or on imaging progression of pre-existing cancer (including new metastasis) is confirmed, it will be determined as a serious adverse event if the severity satisfies any of the criteria specified in Section 10.1.3.

Panitumumab overdose:

When overdose of panitumumab becomes apparent, it should be recorded in the CRF. If adverse event occurs with overdose, it should be recorded as an adverse event in the adverse event column of the CRF.

Furthermore, the overdose of panitumumab is defined as follows.

- 1) Received administration exceeding approved dosage (6 mg/kg) of panitumumab
- 2) Received next administration within 10 days of previous administration

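### Two panitumumab infusions that both respect the ±3-day window in Protocol Table 9.c can be 8 days apart, although Protocol Section 10.1.2 counts a next dose within 10 days as an overdose

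*Protocol*

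**What the plan says.** The schedule is in Protocol Section 9.1. In Table 9.c the protocol-treatment row reads "Day 1, 15, 29 (Day 29 is equal to Day 1 of next course", with an allowance of three days before or after each scheduled day. The table attaches no reason or condition to that allowance.

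Section 8.4 fixes where the next course starts: the day "4 weeks after the starting day of treatment (Day 1) in the previous course will be Day 1 of the subsequent course". The count therefore runs from the previous Day 1, not from the Day 15 infusion actually given. The same section allows a start to be moved earlier or later for holidays and points to Table 9.c.

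Section 10.1.2 defines panitumumab overdose in two ways. The second is "Received next administration within 10 days of previous administration". An overdose is to be recorded in the CRF.

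For suspended panitumumab, Section 8.5.1 describes the dose as postponed, with the word skipped in brackets. It says that "treatment will be resumed after it is confirmed that the subject does not meet the criteria for suspension of panitumumab", with discontinuation if more than 28 days pass after the scheduled day. It gives no resumption day. Section 8.5.2 does give one for TAS-102: if the initiation criteria are met "from Day 13 to Day 28 of the suspension period, treatment will be resumed on Day 29".

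**The concern.** The dosing window and the overdose definition do not fit together. A site can keep both infusions inside Table 9.c and still give a dose that Section 10.1.2 requires it to record as an overdose. Nothing in the visible text of Sections 8.2, 8.4, 8.5.1 or Table 9.c tells it to wait.

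What is at stake is mainly safety and clean records. An infusion after 8 days instead of 14 gives the drug closer together than the every-2-weeks regimen intends. An overdose entry caused by permitted scheduling cannot be told apart, in the CRF, from one caused by a dosing error. The gap in Section 8.5.1 adds some uncertainty, because it concerns patients whose panitumumab was suspended. The listed suspension grounds in Table 8.f are skin disorder and hypomagnesaemia of Grade 3 or higher, after which "treatment at a dose of 6 mg/kg is allowed without dose reduction when it recovers to Grade 2 or less".

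**Working it through.** **Inputs.** Scheduled days 1, 15 and 29, and the ±3-day allowance: Table 9.c. Day 29 counted from the previous Day 1: Section 8.4. Threshold of 10 days: Section 10.1.2. The current protocol version is used. The superseded version and SAP Section 4.1(4) word the treatment row without naming Day 15.

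**The plan's own interval.** 15 − 1 = 14 and 29 − 15 = 14 days, which agrees with dosing every 2 weeks.

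**Day 15 to the next Day 1.** Let a be the deviation of the Day 15 infusion and b that of the Day 29 infusion, each a whole number from −3 to 3.

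Gap = (29 + b) − (15 + a) = 14 + b − a.

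- Shortest: a = 3, b = −3, so 14 − 3 − 3 = 8 days (Day 18, then Day 26).
- Longest: a = −3, b = 3, so 20 days.
- A gap of 10 days or less needs a − b of at least 4.

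| Day 15 given on | Day 29 given on | Gap (days) |
|---|---|---|
| 18 | 26 | 8 |
| 17 | 26 | 9 |
| 18 | 27 | 9 |
| 16 | 26 | 10 |
| 17 | 27 | 10 |
| 18 | 28 | 10 |

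So, of 7 × 7 = 49 combinations, 6 give 10 days or less and 3 give under 10. Whether a gap of exactly 10 days is an overdose depends on how *within 10 days* is read; the first three rows fall inside on either reading.

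**Day 1 to Day 15.** The actual start defines Day 1, so the gap is 14 + a, at least 11 days. There is no conflict here.

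**Would a narrower window do?** The shortest gap with a window of ±w is 14 − 2w. That is 10 days for w = 2, which still touches the threshold, and 12 days for w = 1. Only ±1 day would clear it.

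**Would an 11-day minimum do?** The earliest permitted next infusion is (15 + a) + 11 = Day 26 + a. With a at most 3, that is never later than Day 29. The rule only takes away early starts. In the six rows above the next infusion moves by 3, 2, 2, 1, 1 and 1 days.

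**The case against.** The strongest case against has four parts.

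First, the short gap needs opposite shifts totalling at least 4 days: a late Day 15 and an early next course. Section 8.4 mentions early starts only for holidays, and an early combined start also needs the TAS-102 initiation criteria in Table 8.e to be met early. In the TAS-102 plus bevacizumab study described in Section 4.1.4.2, treatment start was delayed in 68% of subjects. This stands, and it is why the situation is probably uncommon. It does not remove the conflict, because Table 9.c allows the days without condition.

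Second, Section 10.1.2 is a recording definition and not a dosing rule. It does tell sites where the threshold lies, no planned analysis uses overdose, and SAP Section 7.2.7.5 lists every panitumumab date. This also stands, and it limits the consequence. The listing shows a short gap only after it has happened.

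Third, Section 8.0 refers sites to the package insert, and the figures in Sections 8.2 to 8.4 are not reproduced. Either could carry an interval rule. This stands and lowers the confidence.

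Fourth, Section 8.5.1 should not be over-read. A reader might infer that it lets a suspended Day 15 dose be given on, say, Day 20 and be followed by an on-time Day 29, 9 days later. Similarly, Section 8.4 says that "if start of treatment with panitumumab is postponed or discontinued, the starting day of treatment with TAS-102" sets the course, so a delayed Day 1 infusion on Day 6 could be followed by Day 15, again 9 days later. The text does not establish this. Describing the dose as skipped, and speaking of the next dose, can equally mean that the slot is omitted and dosing resumes at the next Day 1 or Day 15. Table 8a fixes those two days, and the study calendars have only Day 1 and Day 15 visits from Course 2. The 28-day limit equals two 14-day slots, so it fits omission as well as re-timing. A Day 15 dose given after Day 18 would also be outside Table 9.c. What remains is an ambiguity to be cleared up, not a second demonstrated way to a short gap.

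**Conclusion.** The conflict holds for the interval from Day 15 to the next course's Day 1. Fully in-window infusions can be 8 days apart, and 6 of 49 day combinations reach 10 days or less. The conclusion rests on the current Table 9.c and on Section 8.4 counting from the previous Day 1.

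Three limits apply. The statement that no minimum interval exists covers only the visible protocol text, so confidence is moderate. The 49 combinations are unweighted, so 6 of 49 must not be read as an expected rate; the documents give no basis for a frequency. Section 8.5.1 is ambiguous, and short gaps could arise there only if a suspended dose may be given between scheduled days.

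The severity is minor. No efficacy or safety analysis depends on it. It is worth correcting because a stated window permits what the protocol itself calls an overdose, and the correction is small.

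**What to change.** Add to Section 8.4, and as a footnote to the protocol-treatment row of Table 9.c: *Consecutive panitumumab infusions must be at least 11 days apart, whatever the ±3-day allowance.*

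Add to Section 8.5.1: *A panitumumab dose missed beyond its window is not made up; dosing resumes at the next scheduled Day 1 or Day 15.*

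Eleven days clears both readings of the 10-day threshold. It still lets either infusion move by the full 3 days when the other is on schedule (Day 18 to Day 29, or Day 15 to Day 26, is 11 days). It is less restrictive than cutting the window to ±1 day.

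The second sentence is needed as well. If make-up doses were allowed under the 11-day minimum alone, a Day 15 dose given on Day 28 could be followed by infusions on Days 39, 50, 61 and 72. That is four consecutive 11-day intervals, a dosing rate 14/11 = 1.27 times the planned one, in a patient just recovered from toxicity.

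The cost is two sentences and a footnote. Sites lose a little freedom when a late Day 15 is followed by an early next course; the next infusion then waits 1 to 3 days and never past Day 29. A patient who recovers just after the window closes waits longer: from Day 19 to Day 29, or from Day 5 to Day 15, is 10 days. The 28-day discontinuation limit still leaves two further slots, for example Days 29 and 43 after a missed Day 15 (43 − 15 = 28).
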